## 12.0 Provisions to Monitor the Data to Ensure the Safety of Subjects

This section is based on the recommendations in NIDA's "Guidelines for developing a Data and Safety Monitoring Plan" as well as NCI's "Essential Elements of a Data and Safety Monitoring Plan for Clinical Trials Funded by the National Cancer Institute."

### ***Summary of the Protocol***

This application consists of a 3-aim proposal. In Aim 1, participants (N=10) will complete usability testing of a depression-specific smoking cessation mobile app, Goal2Quit. Usability testing data will subsequently be utilized to refine Goal2Quit. In Aim 2, the refined Goal2Quit app will be integrated with NRT Sampling (14mg patch and 4mg lozenge, both in original packaging; the standard minimum dose for daily smokers smoking at least 5 cigarettes per day) and examined via a single-arm feasibility test of the integrated intervention (N=10). The goal of feasibility testing is to preliminarily test the integrated Goal2Quit+NRT Sampling intervention to target any potential pitfalls prior to larger-scale testing. In Aim 3, we will conduct a small-scale RCT (N=180) of Goal2Quit + NRT Sampling vs. TAU to provide effect size estimates for a larger RCT.

### ***Trial Management***

The study will be managed from the Addiction Sciences Division within the Department of Psychiatry and Behavioral Sciences at the Medical University of South Carolina (MUSC). Recruitment, data collection, data management, and treatment provision will be coordinated and centrally managed at our research lab at MUSC.

### ***Data Management and Analysis***

Participants will enter data in REDCap, a secure, web-based application designed exclusively to support data capture for research studies. REDCap provides: 1) an intuitive interface for data entry (with data validation); 2) audit trails for tracking data manipulation and export procedures; 3) automated export procedures for seamless data downloads to common statistical packages (SPSS, SAS, Stata, R); 4) procedures for importing data from external sources; and 5) advanced features, such as branching logic and calculated fields. These procedures are effective in minimizing data entry errors (e.g., missing or errant data). The data analysis plan is outlined above.

### ***Quality Assurance***

Accuracy and completeness of the data collected will be ensured by weekly review. The REDCap system does not accept outliers, illogical response patterns, etc. The PI and research assistants will have weekly meetings to discuss any qualitative comments received during data collection and any problems in data collection. The PI will examine the database for potential irregularities monthly. Initial data analyses will examine distributions of variable scores and comparability of baseline characteristics across conditions (for Aim 3) in case analyses need to be adjusted for these. Confidentiality procedures are outlined above.

### ***Regulatory Issues***

This study will be registered on clinicaltrials.gov. The study does not require an IND from the FDA. All serious AEs will be reported to the MUSC Committee on Human Research within 48 hrs. Follow-up of all unexpected and serious AEs will also be reported. All AEs will be reviewed weekly by the PI and yearly by the IRB. Any significant actions taken by the local IRB, and protocol changes will be relayed to the funding agency. We estimate the significant AE rate to be 5% or less. Potential conflicts of interest (COI) will be reported using the SRNT rules for disclosure as well as the rules of MUSC's COI committee.

### ***Trial Safety***

The potential risks and benefits and methods to minimize these risks are outlined in the “Risks to Subjects” section. AEs will be tracked and rated as mild, moderate or severe and as related to NRT by the participant. We will determine if any AEs result in dropouts, or are serious according to FDA guidelines. The PI ([name]) will serve as the Program Manager for AEs. All unexpected AEs will be monitored while they are active to determine if treatment is needed. Since a maximum two-week supply of OTC NRT will be provided, AEs will be rare. Nonetheless, they will be coded on a weekly basis using the FDA’s COSTART rules(82) and entered into a database. For each weekly study meeting, the research assistant(s) will prepare a summary of all AEs, including their severity, whether they caused a dropout, required treatment and presumed relation to drug intake. The PI will review this at the weekly study meeting (or before if more urgent). At the weekly meeting (or before if urgent), research assistants will report any premonitory symptoms to suggest emergence of a serious psychiatric condition (e.g., major depression, suicidality). See “Risks to Subjects” for procedures in place for handling significant clinical deterioration/suicidality. [name], a board-certified Family Medicine physician, will be available on ad-hoc basis for on-site medical supervision for any issues that cannot be resolved by Drs. [name] and [name].

Study procedures will follow as much as possible the FDA’s Good Clinical Practice Guidelines and our research team has found Spilker’s comprehensive text on conducting clinical trials to be useful(83). We will encourage, but not require, participants to notify their physicians that a) they are in a randomized controlled research study examining a treatment for mood and smoking cessation, and b) the physician should contact the PI directly if the physician has any questions.

The research assistants will be instructed not to reveal whether a person is a participant in the study and will report to the PI any outside requests for information about a participant or any breaches in confidentiality. All requests by participant’s physicians and other medical providers will be referred directly to the PI.

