
respond to questions querying their experiences with the intervention including: 1) ease of use, 2) barriers to utilization, and 3) suggested improvements to the treatment.

Measure	Screening	Baseline	1	2	3	4	5	6	7	8	12
PHQ-8	x										
BDI-II		x	x	x	x	x	x	x	x	x	x
Current use of Psychotropic Meds		x	x	x	x	x	x	x	x	x	x
Demographics	x	x									
Smoking History, Including History of Previous Quit Attempts and NRT Use		x									
BADS		x	x	x	x	x	x	x	x	x	x
RPI		x	x	x	x	x	x	x	x	x	x
SHAPS		x	x	x	x	x	x	x	x	x	x
SF-12		x				x					x
Tech Comfort		x									
Utilization of Goal2Quit /Other smoking cessation apps in the last week			x	x	x	x	x	x	x	x	x
Cigarettes per smoking day	x										
Fagerstrom Test of Nicotine Dependence		x									
TLFB (cigarettes, quit attempts, NRT)		x	x	x	x	x	x	x	x	x	x
Contemplation Ladder		x	x	x	x	x	x	x	x	x	x
MTQ Saliency		x	x	x	x	x	x	x	x	x	x
NRT Use			x	x	x	x	x	x	x	x	x
App Feedback (only for those who receive Goal2Quit)			x	x	x	x	x	x	x	x	x

Goal2Quit Usability Scale						x					
Attitudes Toward NRT		x	x	x	x	x	x	x	x	x	x
NRT AEs			x	x	x	x	x	x	x	x	x
Payment		\$10	\$10	\$10	\$10	\$10	\$10	\$10 +\$20 bonus (completing 6 out of 9 surveys)	\$10	\$10	\$10 + \$20 bonus (all surveys completed)

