#### ***Data and Safety Monitoring Plan Administration***

The PI will be responsible for monitoring the trial, with oversight provided by the primary mentor, [name]. The PI will examine monthly the outcomes database for missing data, unexpected distributions or responses, and outliers. The PI will check weekly the AE database prepared by the research assistant(s) immediately prior to the lab meeting a) to see if any particular COSTART categories are being endorsed more frequently than normal and b) to determine if any side-effect symptom checklist scores are higher than expected. A DSM report will be filed with the IRB and funding agency on a yearly basis, unless greater than expected problems occur. The report will include participant characteristics, retention and disposition of study participants, quality assurance issues and reports of AEs, significant/unexpected AEs and serious AEs. We will report efficacy at the end of the trial.

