## **13.0 Risks to Subjects**

This is considered a minimal risk study. Minimal risk means the probability and magnitude of harm or discomfort anticipated in the research are not greater in and of themselves other than those ordinarily encountered in daily life or during performance of routine physical or psychological examinations or tests. The potential risks in this study include those related to: a) clinical deterioration, b) suicidality, c) NRT, d) confidentiality, e) potential data breach from the app database, and f) frustration.

**a) Clinical deterioration:** Depressive symptoms will be monitored via the BDI-II. All participants will complete the BDI-II weekly online and at 12 weeks via a REDCap survey that is accessible via mobile phone, computer, and tablet web browsers. All participants will own an iOS- or Android-compatible smartphone. Thus, all participants will have access to the online BDI-II assessments. [name] and her research team will monitor participant BDI-II scores for possible clinical deterioration (i.e., increasing

depressive symptoms) throughout the course of the study as participants complete the BDI-II. Clinical deterioration will be defined as an increase of 10 or more points on the BDI-II from the baseline BDI-II assessment. In the event that a participant evidences clinical deterioration, [name] will contact the participant via phone and will provide referrals for local mental health resources and/or instruction to go to the ED or call 911 for immediate depression treatment. [name] will suggest that the participant seek treatment and then will follow-up with the participant via phone one week later. In the event that a participant evidences clinical deterioration, the participant will be allowed to continue in the trial, but we will recruit an additional participant for data collection purposes.

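### The only scheduled adverse-event item is NRT-specific and unblinded participants rate relatedness, so non-psychiatric events may be missed and may not be comparable between arms

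*Combined protocol and SAP*

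**What the plan says.** **Who rates.** Section 12.0 (Trial Safety) states that "AEs will be tracked and rated as mild, moderate or severe and as related to NRT by the participant". The same section has research assistants prepare a weekly AE summary, "including their severity, whether they caused a dropout, required treatment and presumed relation to drug intake", which the PI reviews. The study team determines whether an AE is serious under FDA guidelines. Section 13.0 (Protections Against Risk) adds discussion of AEs with a study lead and, if necessary, consultation with a family medicine physician.

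**What is collected.** The schedule table in Section 10.0 has one AE row, *NRT AEs*, at weeks 1 to 8 and week 12. It lists no all-cause AE question.

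**What is promised.** Section 12.0 (Regulatory Issues) has the PI review every AE weekly and states: "We estimate the significant AE rate to be 5% or less". Under Data and Safety Monitoring Plan Administration, the PI checks whether any COSTART category is endorsed more often than normal and also looks "to determine if any side-effect symptom checklist scores are higher than expected". The yearly report covers AEs, significant or unexpected AEs, and serious AEs.

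**Psychiatric safety.** Section 13.0 states: "All participants will complete the BDI-II weekly online and at 12 weeks via a REDCap survey". It also states: "Clinical deterioration will be defined as an increase of 10 or more points on the BDI-II from the baseline BDI-II assessment". Suicidality is monitored through the BDI-II suicidal-thoughts item.

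**The concern.** An NRT-labelled question asks the participant to decide on causation before reporting. Someone who puts a symptom down to something else has no scheduled place to enter it. A TAU participant who uses no NRT may have nothing to enter at all. In the active arm, participants know they were sent NRT and receive brochures describing patch and lozenge AEs, so symptoms of withdrawal or another illness may be credited to the product.

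Two things are at stake. The weekly review and the yearly report may describe a narrower set of non-psychiatric events than they say they cover. And when the PI asks whether a category is more frequent than normal, TAU, the natural reference, may not have been measured on the same basis. The trial is meant to inform a larger RCT, so its AE experience is likely to be carried forward.

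**Working it through.** The plan states no AE calculation, so there is no figure to reproduce. The check is mainly a comparison of sections, with a short calculation for scale.

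**1. Scope of collection against scope of review.** Section 12.0 speaks of AEs without restriction, both in the PI's weekly review and in the research assistants' summary. The Section 10.0 schedule has only the *NRT AEs* row. Section 13.0(c) also places AE assessment through REDCap within its discussion of NRT. Participants are given a study phone number, so spontaneous reports are possible, but no scheduled all-cause question is described. Collection as scheduled is narrower than the review as promised.

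**2. Source of the relatedness judgement.** The participant rates severity and relation to NRT. The allocation is visible: Section 10.0 mails NRT to one arm and only a booklet and study information to the other, and no blinding is described. The weekly staff summary has its own relatedness entry, but no section says whether it is a fresh judgement or repeats the participant's rating, and no causality criteria are given. Seriousness is different: it is assigned to the study team.

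**3. TAU as reference.** The *NRT AEs* row has no arm restriction, whereas the app feedback row in the same table is limited to Goal2Quit recipients. NRT use is asked in both groups at all follow-ups. TAU participants may therefore see the item, but its label gives those who use no NRT little reason to report. What it elicits in TAU cannot be determined from the documents.

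**4. Checklist.** The monitoring plan relies on side-effect checklist scores. No row of that name is in the schedule. It may be the *NRT AEs* item under another name, but the documents do not say so.

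**5. Scale.** Inputs: 100 active and 50 control (Section 11.0); recruitment of 180 at 2:1, so 180 × 2/3 = 120 active (Section 11.0); a prior AE rate of 9% among people who used NRT samples in a quit attempt (Section 13.0(c)). Assumption: every active participant uses NRT in a quit attempt and the 9% carries over.

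- Expected active-arm reporters: 0.09 × 100 = 9, or 0.09 × 120 = 10.8. With partial NRT use the number is lower.
- Exact (Clopper-Pearson) 95% interval for 9/100: 4.2% to 16.4%.
- The TAU rate, b, is not given. Taking b from 0% to 9%, the Wald 95% half-width for the difference is 1.96 × √(0.09 × 0.91/100 + b(1 − b)/50):
  - b = 0%: 1.96 × √0.000819 = 5.6 points
  - b = 5%: 1.96 × √0.001769 = 8.2 points
  - b = 9%: 1.96 × √0.002457 = 9.7 points
- Zero events among 50 TAU participants has an exact 95% interval of 0% to 7.1%.

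A between-arm AE comparison would be imprecise in any case. More participants would narrow these intervals but would not make differently elicited rates comparable.

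**The case against.** The strongest reply is that this is a minimal-risk pilot giving a two-week supply of an over-the-counter product. Safety is neither an aim nor an endpoint, and no between-arm AE analysis is promised. The actual survey wording is not in the documents, so the argument leans on a row label. That limits the size of the point. It does not remove the mismatch between an NRT-labelled item and a promised review of every AE.

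A reader might draw four stronger conclusions. The documents do not support them.

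- *That NRT AEs is the only scheduled safety measure.* The BDI-II is scheduled at baseline and every follow-up for all participants, with set criteria for deterioration and suicidality. Neither criterion depends on attribution to NRT, and TAU is a valid comparator for both.
- *That relatedness is self-attribution alone.* Staff record a presumed drug relation, the PI reviews it weekly, and physician consultation is available. What is missing is a statement of who makes the final judgement and on what basis.
- *That TAU cannot serve as a comparator.* The AE row is not limited to the active arm, and NRT use is asked in both. Comparability is doubtful, not ruled out.
- *That the 5% expectation is an endpoint the trial fails to measure.* It is a planning estimate. The narrower point is that a rate built from an NRT-labelled item is not an all-cause rate.

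On burden, nine follow-ups in 150 to 180 participants give 9 × 150 = 1,350 to 9 × 180 = 1,620 responses. The AE row is already asked at those nine follow-ups, so rewording it adds few survey responses. The real addition is coding work.

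**Conclusion.** The point holds for non-psychiatric AEs. As scheduled, collection is narrower than the review Section 12.0 promises. The first relatedness rating comes from participants who know their allocation, and the status of the staff rating is undefined. Events not attributed to NRT may be missed, and AE rates may not be comparable between arms. Psychiatric safety monitoring and the judgement of seriousness are not affected.

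The size is modest: about 9 to 11 active-arm reporters at most under the assumptions of full NRT use and a transferable 9% rate. How many events would be missed cannot be estimated from the documents. The conclusion assumes that the survey item is as NRT-specific as its label; if the wording is already all-cause, what remains is to say so, name the causality assessor and reconcile the checklist. This is a cheap improvement, not a flaw that threatens the trial's main results.

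**What to change.** 1. In the Section 10.0 schedule, replace the *NRT AEs* row with one all-cause question, worded identically in both arms at every follow-up: any new or worsened health problem since the last survey.
2. Keep the participant's severity and NRT-attribution ratings as separate fields.
3. In Section 12.0 (Trial Safety), state that the PI records the causality judgement, against stated criteria, at the existing weekly AE review, using the physician consultation already provided in Section 13.0 when needed. Seriousness stays with the study team as now.
4. Report AEs descriptively by arm, use TAU as the reference for the monitoring check on frequency, and note that a 100:50 comparison is imprecise.
5. Reconcile the side-effect symptom checklist in the monitoring plan with the schedule: add it as a row, identify it with the AE item, or delete the reference.

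The cost is one reworded item, one extra field and a little more time at a meeting that already takes place. The downside is that more minor, unrelated events will be recorded and need COSTART coding.

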#### ***Data and Safety Monitoring Plan Administration***

The PI will be responsible for monitoring the trial, with oversight provided by the primary mentor, [name]. The PI will examine monthly the outcomes database for missing data, unexpected distributions or responses, and outliers. The PI will check weekly the AE database prepared by the research assistant(s) immediately prior to the lab meeting a) to see if any particular COSTART categories are being endorsed more frequently than normal and b) to determine if any side-effect symptom checklist scores are higher than expected. A DSM report will be filed with the IRB and funding agency on a yearly basis, unless greater than expected problems occur. The report will include participant characteristics, retention and disposition of study participants, quality assurance issues and reports of AEs, significant/unexpected AEs and serious AEs. We will report efficacy at the end of the trial.

## **13.0 Risks to Subjects**

This is considered a minimal risk study. Minimal risk means the probability and magnitude of harm or discomfort anticipated in the research are not greater in and of themselves other than those ordinarily encountered in daily life or during performance of routine physical or psychological examinations or tests. The potential risks in this study include those related to: a) clinical deterioration, b) suicidality, c) NRT, d) confidentiality, e) potential data breach from the app database, and f) frustration.

**a) Clinical deterioration:** Depressive symptoms will be monitored via the BDI-II. All participants will complete the BDI-II weekly online and at 12 weeks via a REDCap survey that is accessible via mobile phone, computer, and tablet web browsers. All participants will own an iOS- or Android-compatible smartphone. Thus, all participants will have access to the online BDI-II assessments. [name] and her research team will monitor participant BDI-II scores for possible clinical deterioration (i.e., increasing

depressive symptoms) throughout the course of the study as participants complete the BDI-II. Clinical deterioration will be defined as an increase of 10 or more points on the BDI-II from the baseline BDI-II assessment. In the event that a participant evidences clinical deterioration, [name] will contact the participant via phone and will provide referrals for local mental health resources and/or instruction to go to the ED or call 911 for immediate depression treatment. [name] will suggest that the participant seek treatment and then will follow-up with the participant via phone one week later. In the event that a participant evidences clinical deterioration, the participant will be allowed to continue in the trial, but we will recruit an additional participant for data collection purposes.

**b) Suicidality:** [name] and her research team will monitor participant BDI-II scores for suicidality, defined as a response of “I would like to kill myself” or “I would kill myself if I had the chance” on the suicidal thoughts or wishes item of the BDI-II at any point during the study, including at baseline. In the event that a participant reports suicidal ideation, [name], a licensed clinical psychologist with 8 years of experience conducting risk assessments with high risk populations (e.g., adults in residential and outpatient substance use treatment, patients in a mood disorders clinic), will complete a risk assessment with the participant via phone. [name] will query the participant for details regarding the suicidal ideation, including a likelihood of harming oneself imminently and a plan for committing suicide. If the participant reports an imminent likelihood of harming him/herself or a plan for committing suicide, [name] will call emergency services and will remain on the phone with the participant until emergency services arrives. In the event that [name] makes contact with the participant (e.g., via phone), the participant expresses an imminent likelihood of harming him/herself, and the connection is lost, [name] will contact emergency services and will provide emergency services with the participant’s contact information, including address. In the event that the participant is not in imminent danger, [name] will provide referrals for local mental health resources and/or instruction to go to the ED or call 911 should suicidal ideation worsen. [name] will suggest that the participant seek treatment and then will follow-up with the participant via phone one week later. In the event that a participant endorses suicidal ideation but is not responsive to [name] phone call within 48 hours, [name] will e-mail the participant a list of local mental health resources and will suggest that the participant seek additional treatment. [name] will also ask that the participant respond to [name] either via phone or e-mail within 24 hours to confirm receipt of the treatment referrals. Should the participant not respond to [name] email within an additional 48 hours (4 days from completion of the assessment) **and** endorse “I would kill myself if I had the chance” on the BDI-II (score = 3 on BDI-II Item 9) [name] will call emergency services and provide emergency services with the participant’s name and address. In the event that a participant endorses suicidal ideation, the participant will be allowed to continue in the trial, but an additional participant will be recruited for data collection purposes.

**c) NRT:** Through brochures delivered as part of the sampling intervention, participants will be educated about lozenge/patch adverse events (AEs) and nicotine intoxication symptoms. We will clearly advise against use of NRT during pregnancy and breast-feeding but we will not require pregnancy tests to be in the study. Female participants will be required to sign a waiver endorsing that: 1) they are not pregnant, 2) they do not plan on becoming pregnant during the study period, and 3) they are using an accepted birth control method. We will not explicitly encourage or discourage use of combined medication (patch+lozenge), though accompanying brochures will advise smokers not to smoke while using NRT product (even though most studies have demonstrated no significant events for combined use). The sampling experience is meant to provide smokers with a real-world opportunity to “test drive” different medications. Our accompanying brochures will discuss the anticipated negative consequences of dual use (nausea, headache) and advise participants to discontinue one or both products should they arise. Participants will be provided with our study phone number and instructed to call our study personnel should they experience such AEs or if they have questions/concerns about NRT use. Given

the 2-week sampling experience, we expect AEs, which will be assessed across follow-up timepoints via REDCap, to be rare and mild. In a prior trial, our group found that 9% of participants who utilized NRT samples in an attempt to quit reported an AE(84). None of these AEs were unexpected, nor did any study participants drop out as a result of an NRT-related AE. Participants will be encouraged to contact [name] as soon as possible for serious AEs and for those conditions that OTC labeling suggests seeing a provider. We will withdraw participants who have a serious AE. For other AEs, if the participant wishes it, the participant will be withdrawn from the study.

This study allows smokers to sample individual or combined NRT products, with a suggestion, though not a requirement, to utilize those products in an attempt to quit smoking. Thus, smokers could be using NRT products concurrently (same day) with smoking. This could result in nicotine intoxication; i.e. nausea, dizziness, headache, stomachache, etc.(85). In a prior study conducted by [name], participants completed a nicotine intoxication scale, and no evidence was found of nicotine intoxication when gum and cigarettes were used concurrently(84). In addition, a review of prior smoking reduction studies indicates that most participants do not have higher than normal cotinine levels with concurrent use of cigarettes and NRT, and few AEs are reported across studies(86).

**d) Confidentiality:** Participants will be made aware of limits to confidentiality at the beginning of screening and when reviewing study procedures/during informed consent which include report of suicidal or homicidal intent or report of abuse or neglect. If the participant reports suicidal or homicidal intent or abuse/neglect, [name] will take appropriate action as outlined by the MUSC IRB, NIH, and the State of South Carolina, which may include contacting the authorities and/or pursuing involuntary commitment at a mental health facility. If participants present no imminent danger but also need more extensive treatment of mental health concerns, they will be given appropriate referrals and instructed to contact their physician.

**e) Data breach from app database:** Although health information will be collected within Goal2Quit (e.g., daily mood ratings, activities, values, use of NRT, etc.), personally identifiable information will not be collected within the app (e.g., name, phone number, email address, etc.), and thus we will neither collect nor retain protected health information (PHI) within Goal2Quit. Upon app download, all participants will be assigned an anonymous username that does not contain personally identifiable information. In the event of a data breach, it is important to note that health information will not be able to be tracked back to specific individual users. By refraining from collection of PHI within the mobile app, we ensure HIPPA compliance while also protecting the identities of our users. In the event of a data breach, all app users will be notified via email.

**f) Frustration:** Participants may become frustrated while completing questionnaires or while using Goal2Quit. Participants will be informed that they may refuse to answer any question(s) that they do not wish to answer and that they may discontinue use of Goal2Quit at any time (which will be tracked as a study outcome).

Since patients will all currently be receiving medical care at MUSC, there are no additional risks associated with participation in this study.

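### The suicidality check starts only from an endorsed answer to one BDI-II item that participants may decline, and no safety action is stated when that item is blank

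*Combined protocol and SAP*

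**What the plan says.** All references are to the Combined protocol and SAP.

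- **Trigger, section 13.0 b).** Suicidality means choosing either of two statements expressing a wish or readiness to kill oneself, "on the suicidal thoughts or wishes item of the BDI-II at any point during the study, including at baseline". A licensed psychologist then "will complete a risk assessment with the participant via phone". Someone not in imminent danger receives referrals and/or ED/911 instruction, and a further call after a week.
- **Unreachable participants, section 13.0 b).** A ladder opens with "In the event that a participant endorses suicidal ideation but is not responsive to" the phone call. An e-mail follows after 48 hours. After another 48 hours emergency services are called, but only for the most severe answer ("score = 3 on BDI-II Item 9").
- **Right to decline, section 13.0 f).** Participants will be told that "they may refuse to answer any question(s) that they do not wish to answer". The suicidality item is not excepted.
- **Deterioration rule, section 13.0 a).** Scores are watched "throughout the course of the study as participants complete the BDI-II". The rule reads: "Clinical deterioration will be defined as an increase of 10 or more points on the BDI-II from the baseline BDI-II assessment". In response, the investigator phones and "will provide referrals for local mental health resources and/or instruction to go to the ED or call 911 for immediate depression treatment", with a second call a week later.
- **Schedule, section 10.0.** The BDI-II is given at baseline, Weeks 1 to 8 and Week 12. The same section refers suicidality procedures to a text called 'Protection of Human Subjects'. No section has that title; section 13.0 appears to be its counterpart.

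**The concern.** The safety rule acts on an answer and is silent on the absence of one. In a safety variable, a missing value is a third state: it is neither a positive nor a negative screen. A participant who declines the item may simply dislike the question or may be reluctant to disclose. The plan does not tell staff to find out which.

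This matters because participants are selected for a PHQ-8 score of 10 or more and followed remotely, and because this item is the only scheduled one that the plan ties to a suicidality risk assessment. What is at stake is participant safety. No endpoint, estimate or sample size depends on it.

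**Working it through.** The plan gives no figure to reproduce here, so the check sets the rules side by side and adds a little arithmetic.

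**1. The three possible states of the item.** Either of the two listed statements leads to a phone risk assessment. Any other answer leads to none. For a blank, nothing is stated.

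**2. When the deterioration rule can act.** BDI-IIs per participant: 1 (baseline) + 8 (weekly) + 1 (Week 12) = 10. The rule compares a later score with baseline, so it can act at 10 − 1 = 9 of them. At baseline, which section 13.0 b) expressly covers, it cannot act.

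**3. How far it backs up a blank at follow-up.** Let s0 be the baseline item score, s the follow-up item score and d the rise on the other items. The rule is met when d + (s − s0) ≥ 10. Take a participant whose true answer would score 3:

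- Answered: d ≥ 10 − (3 − s0). With s0 = 0, d ≥ 7. Section 13.0 b) is triggered anyway, whatever d is.
- Blank, counted as 0 (an assumption): d ≥ 10 + s0. With s0 = 0, d ≥ 10.
- Blank, total left uncomputed (the alternative assumption): the rule cannot be evaluated.

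Under the first assumption the blank raises the required rise by 3 points for any s0. Even when the rule is met, the stated contact is a call with referrals; the risk assessment appears only in section 13.0 b).

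**4. Other places where a blank might be caught.**

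- Sections 11.0 and 12.0 (Data Management and Analysis): entry validation and type and range checks. A mandatory item is not mentioned.
- Section 12.0, Quality Assurance: weekly completeness review, with no participant contact attached.
- Section 12.0, Data and Safety Monitoring Plan Administration: monthly check for missing data, with no participant contact attached.
- Section 12.0, Trial Safety: staff report premonitory symptoms weekly, or sooner if urgent. This needs a symptom to have come to notice.
- Section 13.0 d): action follows a participant's report of intent.
- Section 13.0, Protections Against Risk: action on suicidal ideation, and contact details looked up when deterioration is seen. A blank is not mentioned.

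None of these makes a blank item a reason for contact.

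**5. Workload of a check-in.** The documents give no blank rate. Purely to cost the fix, assume that 0.5% to 3% of administrations stay blank after a prompt.

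- Low count (150 RCT and 10 feasibility participants complete all; 30 and 2 give baseline only): 1,500 + 30 + 100 + 2 = 1,632. At 0.5%, 1,632 × 0.005 = 8.2.
- Full recruitment, no attrition: 180 × 10 + 12 × 10 = 1,920. At 3%, 1,920 × 0.03 = 57.6.
- Section 6.0 ceiling of 240, less 12 usability participants: 228 × 10 = 2,280. At 3%, 2,280 × 0.03 = 68.4.

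That is roughly 8 to 68 contacts over the whole study, under an assumed rate.

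**6. The one-week call (secondary point).** The ladder runs 48 + 48 = 96 hours, or 4 days, which matches the plan's own count from completion of the assessment. It therefore ends about 7 − 4 = 3 days before a one-week call and belongs to the first contact. No step is stated if the one-week call goes unanswered.

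**The case against.** Several objections have force.

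- **A reader might infer that the plan scores a blank as a 'no'.** It does not say so. It reviews completeness weekly and missing data monthly, so blanks may well be seen. What is absent is a written safety action once one is seen.
- **A reader might infer that someone who skips the item is unprotected.** That is too strong. The BDI-II is repeated, a 10-point rise leads to a call, staff report warning symptoms, and section 13.0 d) promises action on reported intent. Each needs some other signal, so none closes the gap.
- **A reader might infer that a flagged participant who later falls silent is abandoned.** The documents do not support this. A participant reached and judged not in imminent danger has had a risk assessment by a licensed psychologist, referrals and/or ED/911 instruction, and a planned follow-up call. Any later qualifying answer restarts the rule. Later survey silence may be ordinary attrition, which section 11.0 assumes at 20%. Pursuing it indefinitely is a preference and is not claimed here.
- **Contact after a refusal sits awkwardly with the right to refuse.** This stands as a real trade-off. It is why the fix is limited to one check-in that may be declined.
- **Unseen text may already deal with this.** Section 10.0 points to 'Protection of Human Subjects', and section 13.0 defers to IRB, NIH and State requirements. This also stands, and it limits confidence.

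**Conclusion.** The concern holds in a limited form. As written, a declined suicidality item leads to no suicidality check. At baseline neither rule can act on it; at the other 9 assessments only the 10-point rule can, and its stated response is not a risk assessment. The 10-against-7-point contrast rests on a true answer scoring 3, a baseline item score of 0 and a blank counted as 0. It illustrates the weakness of the backup and does not measure harm. How often the item would be left blank is unknown.

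The change is worth making because it is cheap and concerns safety; confidence is medium. The unanswered one-week call is a smaller, optional matter. The main point falls if the 'Protection of Human Subjects' text is a separate document that already holds a rule for blank items.

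**What to change.** In section 13.0 a) and b):

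1. Class a blank suicidality item as 'not assessed'.
2. Have REDCap prompt once for that item, keeping the right to decline in section 13.0 f).
3. List any item still blank for the investigator when BDI-II scores are monitored, and again at the existing weekly review.
4. Make one check-in by the phone or e-mail steps already in use. The participant may decline again, and that is recorded.

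Optionally, if a flagged participant does not answer the one-week call, repeat the existing e-mail step.

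The assessment schedule and the conditions for calling emergency services stay as they are, and the clinical response remains the sponsor's decision.

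The cost is one soft prompt, a few sentences and one list at reviews that already take place. Phoning because of a BDI-II result is already a procedure, in section 5.0 for eligibility and section 13.0 for safety. The downside is a small number of extra contacts, some to people who chose not to answer; the true number cannot be given without a blank rate.
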